## 15. HYPOTHESIS TESTS

### 15.1 Treatment Comparisons

Hierarchical testing will be used to preserve the Type 1 error associated with multiple endpoints (per FDA guidance) in pursuit of additional labeling claims beyond the primary efficacy endpoint. Hierarchical testing will not apply to the interim analyses; it will only apply to the final analysis. The testing order follows with two-sided p=0.05 required to continue testing for additional label claims:

#### Primary Outcome Measure:

- 1) Cumulative distribution of the time to respiratory failure resolution with concurrent survival through Day 28 (primary) using all mITT patients.

#### Key Secondary Measure:

- 2) NIAID Ordinal Scale for Clinical Improvement reaches NIAID Score 6-8 by Day 28/exit (primary); percent achieving a NIAID Score 6-8 will be evaluated using all mITT patients; Day 60/exit (confirmatory)

Secondary Outcome Measures (through Day 28 except for survival through both Day 28 and Day 60)

- 3) Time to ICU discharge using all mITT patients
- 4) Time on invasive mechanical ventilation using all mITT patients initially on invasive mechanical ventilation
- 5) Time on non-invasive ventilation using all mITT patients initially on non-invasive ventilation
- 6) Time to hospital discharge using all mITT patients
- 7) Overall survival using all mITT patients
- 8) NIAID area under the curve using all mITT patients
- 9) Multi-system organ failure using all mITT patients.

### 15.2 Primary Hypothesis

The null hypothesis ( $H_0$ ) is that there is no difference in the cumulative distribution (CD) for the time to respiratory failure resolution by Day 28 with Day 28 survival as primary while the alternative hypothesis ( $H_a$ ) is that there is a RLF-100 advantage in the CD:

$$H_0: CD_{RLF-100} < CD_{PLA}$$

$$H_a: CD_{RLF-100} > CD_{PLA}$$

### 15.3 Primary Efficacy Endpoint: Time to Respiratory Failure Resolution

The primary outcome measurement is the cumulative distribution which shows when resolution occurs for

each treatment group. Resolution must last for at least 7 days and start by Day 28; patients must be alive on Day 28. In accordance with the treatment policy strategy, deaths and going on ECMO during the first 28 days are counted as failures; they are counted in the Day 28 denominator to permit the area under the curve to correspond to event-days saved. The mITT patients per treatment group are the respective denominators. The data will be analyzed using a pre-defined proportional hazards model (primary) and unstratified log rank test (secondary); the hazard ratio and two-sided 95% confidence interval will be the critical statistics; in addition, a two-sided 95% confidence interval will be computed for the Day 28 outcome. A 20% absolute improvement in the Day 28 success rate is deemed to be clinically meaningful. A 40% success rate is expected for Placebo + Maximal SOC while a >50% success rate is expected for RLF-100 + Maximal SOC.

Sensitivity analyses are also planned; see Section 13.4. The BDRM will consider the most likely outcome on a patient-by-patient basis. However, a tipping point analysis using the proportional hazard model will be performed where all RLF100-1 patients dropping out will initially be considered as failures while all placebo patients will initially be considered to be successes. The two-dimensional tipping point analysis will shift the balance over the spectrum of all independently being successes and all being failures.

The mITT population will be used for the analysis.

## **15.4 Key Secondary Efficacy Endpoint: Exit NIAID Score Reaches 6-8**

The key secondary outcome measurement is the change in NIAID Score from pre-treatment baseline through Day 28/exit (then Day 60/exit). Deaths are carried forward using NIAID Score=1 while, for withdrawals, the last value before Day 28 (60) is used for the Day 28 (60)/exit outcome. The denominator is fixed per treatment group. The data will be analyzed using a pre-defined logistic regression model (primary) and Fisher Exact test (secondary); the proportion achieving NIAID Score 6-8 by Day 28/exit (primary) and by Day 60/exit (confirmatory) will be presented as the key summary measure to be estimated from the lifetable. A 20% absolute improvement in the Day 28 (and Day 60) percent is deemed to be clinically meaningful. A 40% success rate is expected for Placebo + Maximal SOC while a >60% success rate is expected for RLF-100 + Maximal SOC.

The same two-dimensional tipping point analysis will be conducted as for the primary efficacy analysis except using a logistic regression model.

In addition, a MMRM model using the same covariates will be run for the change from pre-treatment baseline to Day 28/exit using the same baseline covariates for the primary efficacy endpoint. The mean change from pre-treatment baseline to Day 28/exit will be the endpoint of interest. The analyses will be repeated at Day 60/exit (confirmatory). The MMRM model will use an unstructured covariance symmetry will be assumed; in the event that the unstructured covariance structure does not converge, then an autoregressive (1) structure will be tried, and if that does not work, then a Toeplitz structure will be tried. The mean change from pre-treatment baseline to Day 28/exit (primary) and Day 60/exit (confirmatory) will also be of interest.

The mITT population will be used for these analyses.

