### ***NIAID 8-point scale***

The NIAID 8-point scale will be used as a measure of recovery from Critical COVID-19. NIAID Scores will be collected daily through hospital discharge and at Day 28 and at Day 60. All on-study deaths (NIAID Score=1) will be carried through Day 28/exit and Day 60/exit. The distribution of the improvement will be assessed relative to the pre-treatment baseline. The percents achieving a NIAID Score 6-8 by Day 28/exit (primary) and by Day 60/exit (secondary) will be of interest from a regulatory and clinical perspective to be consistent with the remdesivir approval.

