The other time to (favorable) event outcomes will also be assessed using cumulative distributions through Day 28 with an additional evaluation at Day 28; these outcomes include the time to ICU discharge, time on invasive mechanical ventilation, time on non-invasive ventilation, time to discharge alive, and time to resolution of organ failure. These endpoints will be analyzed and displayed the same way as the time to respiratory failure resolution with the exception of just through Day 28. Two-sided 95% confidence intervals will be displayed for the Day 28 success rate differences in the same manner as for the key secondary efficacy endpoint. Any deaths or placement on ECMO on or before Day 28, irrespective of an earlier favorable event, or withdrawals without the favorable event ever occurring will be counted as failures at Day 28; only documented favorable events will be counted as success in the distribution construction and the denominator will include all mITT patient per treatment group. The Day 28 failure imputation allows the cumulative distribution to align with the calculation of mean days saved; thus, patients withdrawing earlier than Day 28 or not reaching a favorable event by Day 28 will be counted as failures at Day 28 in the construction of the time to event lifetables; this is consistent with how favorable events were handled for remdesivir. See Sections 13.3-4 for the handling of intercurrent events and dropouts.

The mean NIAID score will further be displayed over time. The area under the curve will also be calculated and compared using an unpaired t-test. Patients dying prior to Day 28 (then Day 60) will be carried through Day 28 (then Day 60) as being dead (NIAID=1).

The NIAID score will further be assessed for the change from baseline to Day 28/exit and then to Day 60/exit. A mixed model repeated measures (MMRM) containing the same covariates as the primary efficacy endpoint will be performed to explore the impact of modeling serial data; an unstructured covariance symmetry will be assumed; in the event that the unstructured covariance structure does not converge, then an autoregressive (1) structure will be tried, and if that does not work, then a Toeplitz structure will be tried.

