## **15.9 Other Efficacy Endpoint: Blood PaO2/FiO2 Ratio (while on MV)**

Blood PaO2/FiO2 ratio will be analyzed in the same manner as the NIAID Score MMRM model except that data collection stops when invasive mechanical ventilation ends. In addition, the percent improving by at least 100 points will be presented as a descriptive statistic.

The mITT population will be used for the analysis.

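### If the unstructured fit fails, both named fallback covariances for the supportive NIAID MMRM would make the Day 28 standard error too small

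*Combined protocol and SAP*

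**What the plan says.** Sections 14.4 and 15.4 specify an MMRM for change in NIAID score with the same covariates as the primary analysis. Section 14.4 gives the starting covariance: "an unstructured covariance symmetry will be assumed". The first fallback, in both sections, is AR(1): "in the event that the unstructured covariance structure does not converge, then an autoregressive (1) structure will be tried". The second fallback comes into play only when AR(1) has failed as well: "if that does not work, then a Toeplitz structure will be tried". No heterogeneous-variance version, robust standard error or degrees-of-freedom method is given, and no treatment-by-day term is stated.

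On the target of the model, Section 15.4 says: "The mean change from pre-treatment baseline to Day 28/exit will be the endpoint of interest". It repeats the analysis at Day 60.

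On the data, Section 13.7 says: "NIAID Scores will be collected daily through hospital discharge and at Day 28 and at Day 60". Section 15.4 adds: "Deaths are carried forward using NIAID Score=1".

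Section 15.9 reuses the model: the PaO2/FiO2 "ratio will be analyzed in the same manner as the NIAID Score MMRM model", with data stopping when invasive ventilation ends.

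On the role of the model, Section 14.4 presents the MMRM as a way to explore serial data, and Section 15.4 adds it to the logistic regression (primary) and Fisher's exact test (secondary). It is not a step in the testing order of Section 15.1.

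**The concern.** AR(1) and Toeplitz, without a heterogeneous qualifier, each estimate a single variance shared by all visits. Change from baseline cannot have a constant variance here. On Day 2 almost everyone is still at the entry score. By Day 28 the dead sit at 1 and a large fraction is expected at 6 to 8. A shared variance settles near an average over days, so it is too small for the last day, which is the day of interest.

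At stake are the interval and p-value for the Day 28 mean change if a fallback is used: the interval would be too narrow and the p-value too small. The result would stand beside the key secondary endpoint in the report and could be read as corroboration that is stronger than the data support.

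**Working it through.** **Inputs from the documents**
- 198 patients, 132 and 66 (Section 10.7); two-sided 5% (Section 15.1).
- Daily scores, so up to 27 post-baseline days to Day 28 (Section 13.7).
- Key secondary rates: "A 40% success rate is expected for Placebo + Maximal SOC while a >60% success rate is expected for RLF-100 + Maximal SOC" (Section 15.4).
- Mortality of about 50% (Section 6.2).

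The documents state no SD, covariance or error rate for this model, so there is no plan figure to reproduce. The variance profile below is assumed.

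**Step 1: size of the unstructured matrix.** 27 × 28 / 2 = 378 parameters with daily visits; 4 × 5 / 2 = 10 with four visits.

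**Step 2: is a Day 28 variance of this order plausible?** Assume 40% at score 7, 40% dead at 1 and 20% still at 2 or 3. The mean is 0.40 × 7 + 0.40 × 1 + 0.20 × 2.5 = 3.70. The mean square is 0.40 × 49 + 0.40 × 1 + 0.20 × 6.5 = 21.30. The variance is 21.30 − 3.70² = 7.61, against nearly zero on Day 2.

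**Step 3: variance profile.** Daily paths were simulated under the null, with 40% reaching 6-8 and 40% dying in both arms. The residual variance of change was:

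| Day | 2 | 7 | 14 | 21 | 28 |
|---|---|---|---|---|---|
| Variance | 0.12 | 2.52 | 5.45 | 7.19 | 8.77 |

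The plain average of these five is 24.05 / 5 = 4.81, which is 0.55 of the Day 28 value. The AR(1) likelihood fit to all 27 days gave a common variance of 0.54 of the Day 28 value.

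**Step 4: effect on the test.** With complete data and day-specific arm means, the Day 28 estimate does not depend on the covariance chosen; only its standard error does. Hence

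Type I error = 2[1 − Φ(1.96 √(fitted variance / Day 28 variance))].

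With 0.54: √0.54 = 0.735, 1.96 × 0.735 = 1.44, and the result is about 15%. The exact fits gave 15.1% for AR(1) and 14.9% for Toeplitz. The standard error is 1 − 0.735 = 27% too small.

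**Step 5: finite-sample check.** AR(1) REML with 132/66 patients and treatment-by-day terms, 600 runs each:
- Complete data: 15.7% (mean SE 0.33 against a true SD of 0.46).
- Scores missing after discharge: 14.2%.

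The Monte Carlo error is √(0.157 × 0.843 / 600), about 1.5 points. A separately specified set of paths gave 14.8% in 4,000 trials (fitted variance 4.90 against 9.33); using the Day 28 variance instead gave 5.1%.

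**Step 6: range over assumptions**

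| Setting | Type I error |
|---|---|
| Daily visits, varied timing, mortality and recovery: AR(1) | 11.9-17.4% |
| The same: Toeplitz | 11.6-17.3% |
| Daily, SD rising linearly from 0.5 to 2.5 | 17-19% |
| Weekly visits, simulated NIAID paths | 7-14% |
| Weekly visits, all assumed profiles | about 7-16% |
| Treatment main effect only, AR(1), daily | about 2% |

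The last row reverses direction. In the central scenario the model variance is 1.43 times the true variance; 1.96 × √1.43 = 2.34, which gives 1.9%.

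**Step 7: candidate repairs**
- Sandwich standard error for the Day 28 contrast, complete data, 3,000 runs in each of three scenarios: 5.4%, 5.9% and 6.0%.
- Heterogeneous AR(1) with model-based standard errors: 13-19%, because its correlation pattern is also wrong.

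**The case against.** Four objections have force.

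*The fallback may never be used.* A reader might infer that 378 parameters from 198 patients make failure of the unstructured fit likely. The documents do not show this. An unstructured fit needs more patients than days, and 198 far exceeds 27. In 50 simulated trials with about 20% of cells missing after discharge, an unstructured fit by EM maximum likelihood converged to a positive-definite matrix every time. SAS REML could behave differently, but likely failure is not established. The point is therefore conditional: AR(1) matters only if unstructured fails, and Toeplitz only if AR(1) also fails.

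*No label claim depends on it.* A reader might infer that the key secondary endpoint is tested at 12-19%. It is not: logistic regression decides it, and the MMRM is outside the hierarchy. This stands in full.

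*The size and even the direction rest on unstated choices.* Read literally, the covariate list has no treatment-by-day term, and without one the test is conservative. However, a main-effect model has no Day 28 contrast, and Section 15.4 asks for the Day 28 change. The interaction is the natural reading, but the plan should say so. Daily collection also does not prove that every day enters the model.

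*The extension to PaO2/FiO2 was not examined.* The carrying forward of deaths, which drives much of the growth in NIAID variance, has no stated counterpart in Section 15.9. No size can be claimed there.

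Trying AR(1) before the more general Toeplitz is a choice of parsimony. No harm from the order itself was shown.

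**Conclusion.** The concern holds in conditional form. If the unstructured fit fails, either named fallback with model-based standard errors understates the Day 28 standard error of the NIAID change. Type I error for that contrast would be about 12-19% with daily visits or about 7-16% with weekly visits.

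These figures rest on assumed NIAID paths or variance profiles, a treatment-by-day term and no robust standard error. The documents fix the equal-variance fallbacks and the focus on Day 28. They do not fix the numbers.

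The trial's confirmatory error rate is not raised. The severity is minor: a supportive analysis could be reported with too much precision, and a wording change prevents it.

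**What to change.** In Sections 14.4 and 15.4:
- State that the MMRM includes a treatment-by-day term, and list the visits that enter it.
- Require empirical (sandwich) standard errors for the Day 28 contrast under any structure other than unstructured, and name the degrees-of-freedom method. Apply the same rule to the Day 60 repeat.
- Do not rely on heterogeneous AR(1) as the remedy by itself.

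Optionally, fit the model on a few visits, for example Days 7, 14, 21 and 28. The unstructured matrix then has 10 parameters and a fallback should rarely be needed. Apply the same standard-error rule in Section 15.9 for consistency.

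The cost is SAP wording, and Section 14.1 leaves the SAP open until before database lock. Intervals under a fallback become wider, and reducing the visits uses less of the daily data. The sandwich error was checked with complete data only and ran slightly above nominal; its behaviour with scores missing after discharge was not tested.

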## **15.5 Secondary Efficacy Endpoints: Time to Favorable Events**

These secondary efficacy endpoints will be analyzed in the same manner as the primary efficacy endpoint. For each such endpoint, the outcome measurement is the cumulative distribution which is a figure that shows when the favorable event occurs for each treatment group. Any deaths or placement on ECMO on or before Day 28, irrespective of an earlier favorable event, or withdrawals without the favorable event ever occurring will be counted as failures at Day 28; only documented favorable events will be counted as success in the distribution construction and the denominator will include all mITT patient per treatment group. The Day 28 failure imputation permits the area under the curve to correspond to event-days. The denominator is fixed per mITT treatment group. To count in the accruing numerator, the event must be confirmed by the site to last for at least 7 days. The data will be analyzed using the same pre-defined

proportional hazards model (primary) and an unstratified log rank test (secondary); the hazard ratio will be the critical statistic.

The mITT population will be used for the analysis.

## **15.6 Secondary Efficacy Endpoint: Survival**

Kaplan-Meier lifetables for survival will be constructed through Day 28 (primary) and through Day 60 (confirmatory). Survival is defined as not having died as ascertained from the medical record. If death occurs post discharge and prior to Day 28 (or Day 60), study personnel will attempt to obtain a death certificate but may not succeed in the current emergency. A lifetable will be generated; a proportional hazard model will be run to include the four previously stated endpoint covariates (primary) and an unstratified log rank test (secondary) will also be run; the hazard ratio will be the critical statistic. All deaths from any cause are included in the survival analysis as events; the 28-day and 60-day all-cause mortality percents will be estimated from the respective Kaplan-Meier lifetables. The Day 28 and Day 60 estimates from the lifetables will be compared using two-sided 95% confidence intervals.

The mITT population will be used for the analysis.

## **15.7 Secondary Efficacy Endpoint: NIAID 8-point Scale Area Under the Curve**

The NIAID 8-point scale will be used to construct the area under the curve. Deaths will be counted as NIAID Score =1 while the NIAID Score will be scaled by multiplying the AUC times 27/D where D is the number of days on study minus 1. The AUC will be computed for each patient to perform the AUC comparison using an unpaired t-test for the mean difference (and average difference per day).

The mITT population will be used for the analysis.

## **15.8 Secondary Efficacy Endpoint: Multi-system Organ Failure**

The days free of multi-system organ failure will be computed; organs include sepsis, blood, brain, heart, liver, and kidneys. Any such indication constitutes organ failure. The days free of multi-system organ failure will be assessed using the Schoenfeld method. The mean difference is the critical statistic.

The mITT population will be used for the analysis.

## **15.9 Other Efficacy Endpoint: Blood PaO2/FiO2 Ratio (while on MV)**

Blood PaO2/FiO2 ratio will be analyzed in the same manner as the NIAID Score MMRM model except that data collection stops when invasive mechanical ventilation ends. In addition, the percent improving by at least 100 points will be presented as a descriptive statistic.

The mITT population will be used for the analysis.

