## 1. SYNOPSIS

Name of Investigational Product:	RLF-100
Name of Active Ingredient:	Aviptadil
Reference Product(s):	Vasoactive Intestinal Polypeptide (synthetic)
Title of Study:	RLF-100 for the Treatment of Critical COVID-19 with Respiratory Failure
Phase of Development:	Phase 2b/3
Study Site(s):	Multi Center: University of Miami, UC Irvine, Houston Methodist, and others
Total Participant Number:	198 evaluable (mITT) subjects with Critical COVID-19 on mechanical ventilation (for <8 days), non-invasive ventilation or high flow rate nasal cannula at minimum 20L flow and 50% FIO 2
Study Duration:	60-day total follow-up
Background and Rationale:	The research to be conducted under this protocol references Phase 1 research conducted under IND 52,088 in which Vasoactive Intestinal Polypeptide (VIP) has previously shown suggestions of efficacy in the treatment of ARDS related to sepsis, pulmonary arterial hypertension and other respiratory disorders.
Objectives:	To demonstrate the efficacy of RLF-100 in improving survival and reducing respiratory distress / requirement for mechanical ventilation in patients with Critical (NIH/FDA definition) COVID-19 receiving maximum standard of care other than extracorporeal membrane oxygenation (ECMO).
Endpoint(s):	
Primary Outcome Measure:
 
 
1) Cumulative distribution of the time to respiratory failure resolution with concurrent survival through Day 28.
 
 
Key Secondary Measure:
 
 
2) NIAID Ordinal Scale for Clinical Improvement (Scores 6-8) through Day 28
 
 
Secondary Outcome Measures (through Day 28 unless otherwise specified):
 
 
3) Survival lifetable through Day 28 and through Day 60
 
4) Time to ICU discharge
 
5) Time on invasive mechanical ventilation
 
6) Time on non-invasive ventilation
 
7) Time to discharge alive
 
8) Multi-organ failure free days
 
9) NIAID Area under the curve (AUC)
 
 
Other Outcome Measures (through Day 28):
 
 
10) Respiratory Distress while on mechanical ventilation: Blood PaO2/FiO2 ratio [Time Frame: enrollment through extubation]
 
11) Oxygenation Index
 
12) Improvement in chest x-ray
 
13) IL-6, TNF<math>\alpha</math> and other inflammatory markers
 

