## 9.2

### Inclusion Criteria

All patients entered this trial will have the diagnosis of Critical COVID-19 (test positive in past 7 days). Subjects will be observed for a 1 to 24-hour period, during which time all inclusion criteria must be met. If all criteria are met once (not necessarily simultaneously), the patient will be enrolled and randomized to receive the study drug or placebo within 12 hours of the following entry criteria being fulfilled:

- 1) Critical COVID-19 with respiratory failure by NIH/FDA definition requiring either mechanical ventilation, non-invasive ventilation, or high flow rate nasal cannula at minimum 20L flow and 50% FIO2.
- 2) Physician commitment to maximal Standard of Care treatment – as deemed necessary
- 3) Primary cohort: patients with less than 8 days of exposure to mechanical ventilation, non-invasive ventilation, or high flow rate nasal cannula at a minimum of 20L flow and 50% FIO2.

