### ***Index of Respiratory Distress***

The PaO2/FiO2 ratio shall be calculated from the continual telemetry data obtained from the ICU information system and arterial blood gas (ABG) for patients while on mechanical ventilation. This variable is not useful after O2 on mechanical ventilation has been reduced because the ratio is reduced even though oxygenation is already improving. In the absence of an arterial line, ABG's will be collected only when medically indicated.

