## 21. APPENDIX A; SCHEDULE OF EVENTS

Schedule of Events: Appendix A		Day 1		Day 2		Day 3		Day 4	Day 5	Day 6	Day 7	Day 8- Day 27	Day 28		Day 60
Procedures	Screening	1st Dose a	During infusion	2nd Dose a	During infusion	3rd Dose a	During infusion	Follow- Up	Follow- Up	Follow- Up	Follow- Up	Follow- Up	Follow-Up D28 or day of discharge	Day 28 Follow- up Phone Call	Day 60 Follow- up Phone Call
Informed Consent Process	X														
Evaluation of Exclusion & Inclusion Criteria	X														
Medical History/Demographics	X														
Confirm Eligibility and Randomization		X													
Vital Signs (Pulse, Respirations) b	X	X	X b	X	X b	X	X b								
Blood Pressure c	X	X		X		X									
Weight	X	X		X		X		X	X	X	X		X		
CNS Assessment	X	X		X		X		X	X	X	X		X		
Urine Output and Fluid Intake		X		X		X		X	X	X	X				
IV Administration of Study Drug		X	X	X	X	X	X								
ICU Telemetry: ECG		X		X		X		X	X						
PaO 2 /FiO 2 Ratio	X	X		X		X		X	X	X	X		X		
CBC (Complete Blood Count with Differential & Platelets)	X	X		X		X		X	X	X	X		X		
CMP (Complete Metabolic Panel)	X	X		X		X		X	X	X	X		X		
ABG - Non-ventilated subjects (for PaO 2 /FiO 2 ratio): pH, pCO 2 , pO 2 , CO 2 , HCO 3 per ICU protocol	X								X			X g			

Schedule of Events: Appendix A		Day 1		Day 2		Day 3		Day 4	Day 5	Day 6	Day 7	Day 8- Day 27	Day 28		Day 60
Procedures	Screening	1st Dose a	During infusion	2nd Dose a	During infusion	3rd Dose a	During infusion	Follow- Up	Follow- Up	Follow- Up	Follow- Up	Follow- Up	Follow-Up D28 or day of discharge	Day 28 Follow- up Phone Call	Day 60 Follow- up Phone Call
ABG - Ventilated subjects (for PaO 2 /FiO 2 ratio): pH, pCO 2 , pO 2 , CO 2 , HCO 3 per ICU protocol h	X	X	X	X	X	X	X	X	X	X	X	X	X		
Murray Score	X	X		X		X		X	X	X	X		X		
D-Dimer	X	X		X		X		X	X	X	X		X		
PT/INR/aPTT	X														
Lactic Acid	X	X		X		X		X	X	X	X		X		
Serum/Urine Pregnancy Test (Either Serum or Urine, not both)	X														
HIV (based on history, no HIV testing is required)	X														
Cytokines: Circulating IL6 e,j		X	X e	X	X e	X	X e		X		X		X		
Cytokines: TNFa e,j		X	X e	X	X e	X	X e		X		X		X		

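### PaO2/FiO2 is analysed only on invasive ventilation, for a reason that runs against the arithmetic, and who contributes data depends on post-randomisation events

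*Combined protocol and SAP*

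**What the plan says.** The Synopsis lists PaO2/FiO2 as item 10, under other outcome measures, with "Time Frame: enrollment through extubation". Section 15.9 analyses it with the mixed model used for the NIAID score, "except that data collection stops when invasive mechanical ventilation ends". It adds a descriptive percentage of patients gaining 100 points or more, and closes: "The mITT population will be used for the analysis".

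Section 13.7 (Index of Respiratory Distress) derives the ratio from telemetry and "arterial blood gas (ABG) for patients while on mechanical ventilation". It says the ratio loses its usefulness once oxygen on the ventilator has been lowered, "because the ratio is reduced even though oxygenation is already improving". Without an arterial line, gases are taken only on medical indication.

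Four other parts of the plan bear on this:

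- Section 9.2 admits patients "requiring either mechanical ventilation, non-invasive ventilation, or high flow rate nasal cannula".
- Section 15.1 (items 4 and 5) confines each ventilation-time endpoint to patients who start on that type of support. Section 15.9 has no such limit.
- Section 14.4 applies the treatment-policy strategy to all analyses. Section 13.3 exempts only terminal events, naming death and ECMO, and its failure rule for them covers time-to-event outcomes.
- Appendix A schedules the ratio at Screening, on Days 1 to 7 and on Day 28 or discharge. A separate row, "ABG - Non-ventilated subjects", is marked as serving this ratio at Screening, Day 5 and (footnote g) Day 10.

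**The concern.** The ratio's denominator is FiO2, so the reason given for the restriction appears to run the wrong way.

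The restriction also ties observation to response. Extubation is an outcome the drug is meant to bring about, and it ends a patient's data. A patient who enters on high-flow oxygen or non-invasive ventilation has no invasive-ventilation values to contribute unless intubated later, which is an unfavourable outcome. The groups compared on a given day are then not the groups as randomised. If the drug speeds extubation, the patients still ventilated in its arm are a more selected and sicker remainder, and a real oxygenation benefit could be understated. The percentage gaining 100 points has the same weakness, because a patient extubated early loses the chance to record the gain and no denominator is stated.

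**Working it through.** The plan states no figure for this outcome, so there is none to reproduce.

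**1. Direction of the ratio.** P/F = PaO2/FiO2. At PaO2 80:

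- FiO2 0.8: 80/0.8 = 100
- FiO2 0.5: 80/0.5 = 160
- FiO2 0.4: 80/0.4 = 200

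The ratio falls only if PaO2 drops by a larger fraction than FiO2, that is by more than 1 − (new FiO2/old FiO2). From 0.8 to 0.5 this is 1 − 0.5/0.8 = 37.5%. From 0.5 to 0.4 it is 1 − 0.4/0.5 = 20%. A fall in PaO2 of that size is not improving oxygenation, so the Section 13.7 reason is backwards at stable or improving PaO2.

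**2. Who contributes.** Section 9.2 brings in three kinds of support, Section 15.9 accepts data from one of them, and its population is all mITT patients. Section 15.1 shows that the plan limits by initial support when it intends to. The wording also differs: Section 13.7 says mechanical ventilation, Section 15.9 says invasive, and Section 11.1 counts CPAP and BiPAP as non-invasive mechanical ventilation.

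**3. Estimand.** Extubation is not terminal and a ratio can still be measured after it. Under Sections 13.3 and 14.4 later values should be used, but Section 15.9 stops collecting them. For death and ECMO, the NIAID model cannot simply be copied: it carries deaths forward as score 1 (Section 15.4), and the ratio has no equivalent.

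**4. Size, by illustration.** All inputs are assumed:

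- 20,000 patients per arm and eight daily values; half the patients invasively ventilated at entry
- baseline mean 150 (SD 45); placebo slope 6 points/day (SD 6); residual SD 25
- drug adds 6 points/day, so the last-day difference is about 6 × 7 = 42
- extubation above 220, intubation below 110; no deaths

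The model-type estimate is a normal maximum-likelihood fit by arm with unstructured covariance and no covariates.

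| Moves on/off ventilator follow | Later intubations join | All patients | Raw, on ventilator | Model-type | Contributing on last day, drug v placebo |
|---|---|---|---|---|---|
| Previous day's ratio | No | 41.7 | 22.4 | 40.6 | 20% v 29% |
| Previous day's ratio | Yes | 42.5 | 24.8 | 43.3 | 31% v 46% |
| Same-day ratio, unrecorded if the patient is then off the ventilator | No | 41.7 | 16.5 | 21.3 | 17% v 27% |
| Same-day ratio, as above | Yes | 42.5 | 19.1 | 26.2 | 25% v 43% |

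In the last two rows the model-type fit keeps 21.3/41.7 = 51% and 26.2/42.5 = 62% of the difference. With no drug effect it gave −0.1 to 0.4 across the four settings. With drug effects of 3, 6 or 10 points/day, every estimate kept the right sign.

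**The case against.** The strongest reply is that this is a minor, openly labelled outcome. The Synopsis and Section 15.9 both say it is measured on the ventilator, and none of the nine items in the Section 15.1 hierarchy uses it. That stands. A reader might infer from the Synopsis objective of "improving survival and reducing respiratory distress / requirement for mechanical ventilation" that the respiratory-distress aim depends on this ratio. The documents do not support that. The Section 7 objectives are time to respiratory failure resolution and NIAID score, and the primary endpoint and the ventilation-time endpoints also serve the Synopsis phrase.

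Second, the Section 13.7 sentence concerns oxygen being lowered on the ventilator and does not expressly explain stopping at extubation. That is fair, but it is the only reason given for limiting the ratio, and it is still wrong.

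Third, entry through later intubation is an inference. No text says how such patients are handled, and a time frame from enrolment to extubation could mean only those ventilated at enrolment. This also stands. The defect is that Section 15.9 leaves the matter open.

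Fourth, a mixed model can deal with extubation that recorded values predict, and Appendix A (footnote h) gives ventilated patients daily gases. That holds in the first two rows of the table. It is not assured: Section 13.7 itself lists reasons for removing ventilation, such as comfort care or resource allocation, that recorded ratios need not capture.

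Fifth, off-ventilator gases are taken per ICU protocol, or only on medical indication without an arterial line. A comparison of all patients is therefore itself selective. This stands and limits the remedy.

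**Conclusion.** The point holds for an outcome outside the hierarchy. The stated reason is arithmetically wrong at stable or improving PaO2. Section 15.9 lets post-randomisation events decide who contributes, against Sections 13.3 and 14.4, and gives no rule for death or ECMO.

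The size depends on assumptions. The planned type of model may lose almost nothing, or about 38% to 49% of a benefit (100% less the 62% and 51% above), according to whether extubation follows recorded or unrecorded ratios. The documents do not settle which applies. The raw on-ventilator differences in the table shrink more, but they are not the planned analysis and should not be quoted as its bias.

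Two further readings are tempting and unsupported. A reader might infer that the comparison could reverse or produce a false positive; neither appeared in these simulations. A reader might also infer that the ratio is never measured off the ventilator; Appendix A schedules it there, so the restriction lies in the analysis. The primary and hierarchical results are untouched.

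**What to change.** - **Section 13.7:** delete the sentence giving the reason, and use one term for the type of ventilation meant.
- **Section 15.9:** limit the on-ventilator mixed model and the percentage gaining at least 100 points to mITT patients on invasive ventilation at randomisation. Use that number as the fixed denominator and label both analyses descriptive.
- **Supportive analysis:** use all recorded ratios in all mITT patients regardless of ventilation status, rank-based and adjusted for baseline ratio, with death and ECMO ranked worst.
- **Reconcile** Sections 13.7 and 15.9 with the Appendix A rows for the ratio and for non-ventilated blood gases.

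The cost is SAP wording, with no visits added. The limitation is that off-ventilator gases will be incomplete and selectively taken: outside Screening, Day 5 and Day 10, no gas is scheduled for non-ventilated patients. The all-patient analysis should therefore stay supportive, with missingness reported by arm and day.
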